#### 10.2 Analysis

Population: SCR

Stratification: Table: NA

Listing: By patient no.

Statistics: Patient's disposition and early withdrawal will be summarised (frequency and percentages based on patients received the first dose of Brolucizumab) for all categories except the screened, screen failure, enrolled, patients enrolled but not received the first dose of Brolucizumab will be summarised (frequency) by total for table. The listing will be provided for the patient's disposition status and early withdrawal patients separately.

#### 11. Participant demographics and other baseline characteristics

#### 11.1 Variables and derivations

The following demographic and other baseline characteristics will be summarized by treatment group:

- Age (Years)
- Gender (Male and Female)
- Nationality
- Race
- Ethnicity
- Height (cms) at Screening
- Weight (kgs) at Screening
- Smoking history (Current Smoker, Past Smoker and Never Smoker)
- Baseline value of BCVA
- Risk factors and ocular disease related history
- Patients with treatment for nAMD received in the 12 months prior to study entry

Population:	For Table: FAS
	For Listing: SCR
Stratification:	Table: NA
	Listing: By patient no.
Statistics:	Demographic and other baseline characteristics will be summarized
	for table and presented in data listings.

#### 12. Exposure and Compliance to the study treatment

#### 12.1 Variables and derivations

In "Brolucizumab dosing" eCRF form treatment dosing related data will be captured. The following parameters will be summarised for treatment exposure:

- Number of patients received Brolucizumab dose by visit
- Number of patients received the doses under q8w dosing interval
- Number of patients received the doses under q12w dosing interval
- Number of patients received all planned doses.
- Duration of exposure between first and last doses (Days)

The parameter "Compliance with overall treatment" will be summarised for treatment compliance.

Patient will be considered compliant with overall treatment Brolucizumab if they received the scheduled administration of all doses within the schedule visits and time window.

Population:	For Table: FAS
	For Listing: SCR
Stratification:	Table: NA
	Listing: By patient no.
Statistics:	Treatment exposure and compliance will be summarised (frequency
	and percentages) for table and the listing will be presented.

#### 13. Medical and treatment history

#### 13.1 Variables and derivations

Medical history data will be coded using the MedDRA central coding dictionary, Version 24.1 or later.

The following parameters will be summarised for the subject's medical history as mentioned in eCRF.

- Number of patients with at least one medical history
- Number of patients for each medical history by SOC and PT

Population:	For Table: FAS
	For Listing: SCR
Stratification:	Table: NA
	Listing: By patient no. and alphabetically for SOC and PT within each
	SOC
Statistics:	Medical history will be summarised (frequency and percentages) for
	table. Medication History for nAMD will also be presented in the table
	separately. Listing will be provided.

#### 14. Prior and Concomitant medications

#### 14.1 Variables and derivations

In eCRF "Prior and Concomitant Medications" form concomitant medication related data will be captured.

All prior and concomitant medications entered into the database will be coded using the WHODD B3, dated September 1, 2021 or later. Preferred ATC coding will be applied to medications.

'Prior medications' are defined as any medication started and ended prior to first administration of the Brolucizumab dose.

Concomitant medications are defined as any medication taken after or on the first administration of the Brolucizumab dose till the end of the trial or any medication taken prior to the first Brolucizumab dose administration and having "ONGOING" status at the first administration of the Brolucizumab dose.

In section 24 Appendix 2 the algorithm is given for calculation of partial date imputation for Concomitant Medication, and it will be used for partially missing Concomitant Medication start and end date imputation.

The following parameters will be summarised for the patient's prior and concomitant medication:

- Number of patients with at least one prior and concomitant medication
- Number of patients for each prior and concomitant medication by ATC-2 and PT.

#### Derivations:

All medications captured on the "Prior and Concomitant Medications" form of the eCRF will be categorised (prior and concomitant medication) as follows:

- If the medication end date is less than the first Brolucizumab dose administration date, then respective medication will be considered as "Prior Medication".
- If the medication start date or end date is greater than or equal to the first Brolucizumab dose administration date or if the medication start date is less than the first Brolucizumab dose administration date and medication is marked

as "ONGOING" then respective medication will be considered as "Concomitant Medication".

Population:	For Table: FAS
	For Listing: SCR
Stratification:	Table: by descending frequency of ATC-2 level and PT within each
	ATC-2 level
	Listing: By patient no. and start date
Statistics:	Prior and concomitant medication will be summarized as (frequency
	and percentages) for table and listing will be provided. In addition, the
	number and percentage of patients receiving rescue medications and
	significant non-drug therapy will be summarized by preferred term
	(coded by WHO ATC classification) and the same will be listed.

#### 15. Adverse events

#### 15.1 Variables and derivations

Adverse Events (AEs) will be coded using medical dictionary for regulatory activities (MedDRA) terminology, Version 24.1 or later.

An AE is any undesirable sign, symptom or medical condition occurring after starting study treatment, even if the event is not considered to be treatment related.

The following parameters will be summarised for the overview of patient's adverse events:

- Incidence of AEs
- AEs related to Brolucizumab
- Ongoing AEs (if applicable)
- CTCAE grade of AEs
  - o Mild
  - o Moderate
  - o Severe
  - Life Threatening
  - Death Related to AE
- Serious adverse event
- Serious AEs related to Brolucizumab
- AEs Action Taken
  - o No action taken
  - Investigational treatment permanently discontinued due to this adverse event
  - Concomitant medication given
  - Non-drug therapy given
  - o Patient hospitalized/ patient hospitalization prolonged
- Outcome of AEs
  - Not Recovered or Not Resolved
  - Recovered or Resolved
  - Recovering or Resolving
  - Recovered Or Resolved with Sequelae
  - o Fatal
  - o **Unknown**

- AEs leading to Discontinuation from the study
- AEs leading to Death
- Related AEs leading to Death

The overview of serious adverse events will also be summarised using the abovementioned parameters with one additional "seriousness criteria" category which includes (death, life threatening, Involved or prolonged inpatient hospitalization, Results in persistent or significant disability / incapacity, Congenital anomaly/birth defect, medically significant event) will be provided in the table.

#### Derivations:

- The question "Relationship to study drug" is answered as "Yes" then respective AEs will be considered as Related AE.
- The question "Was the adverse event serious" is answered as "YES" then respective AE will be considered as serious AEs.
- Subject's primary reason for discontinuation is "Adverse Event" then we will consider it as AEs leading to Discontinuation from the study.
- Subject's primary reason for discontinuation is "Death" or AE Outcome is "FATAL" then we will consider it as AEs leading to death.
- Subject's primary reason for discontinuation is "Death" or AE Outcome is "FATAL" and "Relationship to study drug" is answered as "Yes" then we will consider it as Related AEs leading to death.

#### 15.2 Analysis

Uncoded adverse events category will be added in the AEs by SOC/PT summary tables if applicable.

The analysis of incidences of TEAEs, Ocular and systemic AEs, Suspected AEs related to the study medication, Serious AEs, AEs leading to death, AEs leading to discontinuation from the study by primary system organ class and preferred term is covered in the primary endpoint section 19.

#### 15.2.1 Overview summary for AEs and SAEs

Population:	For Table: FAS
	For Listing: SCR
Stratification:	Table: NA.
	Listing: By patient no.
Statistics:	An overview summary will be presented as (n=number of patients,
	m=number of events and %=percentage of patients) for table. The
	listings will be presented

# 15.2.2 Incidence of serious adverse event, AEs suspected to be related to the study drug, AEs leading to discontinuation from the study, TEAEs leading to death by severity

- Population: For Table: FAS
  - For Listing: SCR
- Stratification: Table: by descending frequency of SOC and descending frequency of PT within each SOC and severity.
- Statistics: All AEs categories mentioned above will be summarized for table.

#### 16. Safety laboratory tests

The Safety laboratory data will not be applicable for this study.

#### 17. Vital signs

#### 17.1 Variables and derivations

In "vital signs" eCRF form vital signs at baseline related data will be captured.

The following vital signs will be reported for this study:

- Heart rate (bpm)
- Systolic blood pressure (mmHg)
- Diastolic blood pressure (mmHg)

The qualitative measurements of vital signs will be categorised as (Normal, Abnormal Clinically Significant and Abnormal Not Clinically Significant)

17.2	Analy	sis
Populat	tion:	For Table: FAS
		For Listing: SCR
Stratific	ation:	Table: NA
		Listing: By patient no. and visit
Statistic	cs:	The quantitative and qualitative data will be summarized in
		table. listing will be presented.

#### 18. Physical examination

#### 18.1 Variables and derivations

In "Physical examination" eCRF form physical examination at baseline related data will be captured.

The physical examination including the following body systems will be examined:

- Ears, Eyes, Nose, Throat and Neck
- Lymph nodes
- Lungs
- Heart
- Abdomen
- Skin
- Extremities
- Neurological System
- Musculoskeletal Systems
- Other

These measurements will be categorised as (Normal, Abnormal Clinically Significant, Abnormal Not Clinically Significant and Not Done)

Population:	For Table: FAS
	For Listing: SCR
Stratification:	Table: NA
	Listing: By patient no. and visit
Statistics:	Physical examination data will be summarized (frequency and
	percent) and listed.

#### **19. Primary endpoint assessments**

The primary endpoint will evaluate the safety of intravitreal brolucizumab in real-world patients with nAMD.

# 19.1 Incidence and characteristics of treatment-emergent adverse events during the 56 weeks of treatment with brolucizumab

#### **19.1.1** Variables and derivations

#### Variables:

The following incidences of TEAEs during the 56 weeks of treatment and its characteristics will be reported:

- Incidences of TEAEs
- Ocular and systemic AEs
- Suspected AEs related to the study medication
- Serious AEs
- AEs leading to death
- AEs leading to discontinuation from the study

#### Derivation:

- Timeframe: The first brolucizumab administration date to Visit 11 (week 56)
- If the question from eCRF, "Treatment Emergent AE" = "Yes", then corresponding events will be considered as TEAEs.
- Ocular and systemic AEs.
- If the question from eCRF, "Relationship with study drug" = "Yes", then corresponding events will be considered as suspected AEs related to the study medication.
- If the question from eCRF, "Was the adverse event serious" = "Yes", then corresponding events will be considered as serious AEs.
- If the question from eCRF, "What is the outcome of this adverse event" = "Fatal", then corresponding events will be considered as AEs leading to death.
- If the question, "Primary Reasons for Discontinuation" = "Adverse event", then corresponding events will be considered as AEs leading to discontinuation from the study.

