#### 7.3.7 Data collection schedule

Data originating from routine patient visits and assessments at study time points (Baseline, i.e. start of brolucizumab treatment, and approximately week 4, week 8, week 16, week 20, week 24, week 32, week 40, week 44, week 48 and at week 56 post-initiation of treatment/or discontinuation of treatment) and safety data (AEs and SAEs, see Section 8) from any time point during the duration of the study will be recorded for the purpose of this study. Data will be collected only on the eye treated with brolucizumab and if both eyes are treated with brolucizumab, the data from one eye (study eye) will be recorded. The selection of eye (study eye) will be as per discretion of the Investigator at the time of enrolment in this study.

Participation in this prospective interventional study and confirmation of patient consent to collect and use patient data will be documented using an informed consent form by the site staff on or before the baseline visit. A copy of this signed document will be given to the patient and the original will remain in the patient's records.

Each patient is uniquely identified in the study by a combination of the Investigator's center number and a patient number. The center number is assigned by Novartis (or designee), the patient number is assigned by the Investigator. At each site, the first patient is assigned patient number 1, and subsequent patients are assigned consecutive numbers (e.g., the second patient is assigned patient number 2; the third patient is assigned patient number 3, and so forth). Once assigned to a patient, the patient number will not be reused.

Visit number	1	2	3	4	5	6	7	8	9	10	11
Time of visit [Week (Wk)]	Wk 0	Wk 4±1	Wk 8±1	Wk 16±1	Wk 20±1	Wk 24±1	Wk 32±1	Wk 40±1	Wk 44±1	Wk 48±1	Wk 56 (Follow-up) EOS
Inclusion/ Exclusion Criteria	Х										
Informed consent	Х										
Demographics and Baseline Characteristics	X										
Physical Examination	Х										
Vital Signs	Х										
Brolucizumab	Х	Х	X	X*	X #	X*	X*#	X*	X#	X*	
BCVA	Х	Х	Х	X*#	X #	X*	X*#	X*	X #	X*	X
ІОР	Х	Х	Х	X*#	X #	X*	X*#	X*	X #	X*	Х
Fundus photography	Х			X*#			X*#				Х
ОСТ	Х	Х	Х	X*#	X #	X*	X*#	X*	X #	X*	X
Fluorescein Angiography (FA)	X										Х
Adverse Events	Х	Х	X	X*#	X #	X*	X*#	X*	X #	X*	X

Table 7-1	Data collection	
-----------	-----------------	--

\* - q8w dosing

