#### 7.6.5 Safety and Effectiveness analysis

#### **Primary Endpoint Analysis**

• Incidence and characteristics of treatment-emergent adverse events during the 56 weeks of treatment with brolucizumab would be evaluated.

Safety of brolucizumab treatment will be assessed by reported (ocular and systemic) adverse events (AEs). The incidence of AEs (new or worsened after the start of brolucizumab) will be summarized by MedDRA primary system organ class and preferred term. Similar summaries will be provided for fatal AEs and other serious AEs, AEs causing discontinuation of study drug, and AEs suspected to be related to the study medication (as assessed by the Investigator). Furthermore, AEs will be summarized by primary system organ class, preferred term and severity. Incidence rates will also be determined per treatment year, both for the first occurrence of an event and total events. An adverse event management protocol/mitigation plan would be provided to all the investigators to manage an event of intra-ocular inflammation.

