#### 7.9 Other aspects

Every patient has the right to discontinue study participation at any time, and every patient may be discontinued from the study for any reason beneficial to his/her wellbeing. All data generated up to the time of discontinuation from the study will be analyzed and the reason(s) for discontinuation/withdrawal will be recorded.

Patients must be discontinued from the study in the case of:

- Withdrawal of informed consent to collect or use their data
- Significant safety risk
- The Investigator must record the discontinuation/withdrawal reason in the Case Record Form (CRF). Reasons that a patient discontinues treatment and participation from the study are considered to constitute one of the following:
- Adverse event(s)
- Unsatisfactory therapeutic effect
- Subject's condition no longer requires study treatment
- Subject withdrew consent
- Lost to follow-up
- Administrative problems
- Death

Patients who discontinue brolucizumab treatment should be asked to return for an early discontinuation assessment. For patients who are lost to follow-up (i.e. those patients whose status is unclear because they fail to appear for study visits without stating an intention to withdraw), the Investigator should show "due diligence" by contacting the patients and asking them to return for a final assessment. Every effort should be made to obtain the reason for discontinuation.

The Investigator should document in the source documents steps taken to contact the patient, e.g. dates of telephone calls, registered letters, etc.

For the purpose of this study, the study drug brolucizumab will be provided free of costs for the patients in this study.

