#### 10. Participant disposition and withdrawal

#### 10.1 Variables and derivations

End of trial classifications are defined as follows:

- Screening failure: Patient signed an informed consent form but has not satisfied inclusion and exclusion criteria.
- Enrolled Patients: Patient signed an informed consent form and has satisfied inclusion and exclusion criteria.
- Discontinued patients: patients who discontinued the trial, as indicated in the "Study Completion" eCRF form, will be assumed to be discontinued patients
- Completed trial: Patients who completed the trial, as indicated in the "Study Completion" eCRF form, will be assumed to have completed the trial.

The following parameters will be summarised for the patient's disposition table as per eCRF

- Number of screened patients
- Number of screening failure patients
- Number of enrolled patients
- Number of patients enrolled but not received the first dose of Brolucizumab
- Number of patients received all dose of Brolucizumab
- Full analysis Set (FAS)
- Number of completed patients
- Number of discontinued patients

Patient's primary reason for discontinuation (reasons mentioned in eCRF study completion form) which is as follows:

- Adverse event
- Unsatisfactory therapeutic effect
- o Subject's condition no longer requires study treatment
- Subject withdrew consent
- Lost to follow-up
- Administrative Problems
- Switch Agent
- o Death
- o Other

Derivation:

- If patient status is indicated as "screen failure" in the eCRF screen failure form, then respective patients will be counted as screen failure.
- If the question "Was written informed consent obtained" = "Yes" from the informed consent eCRF form and the question "Did the subject meet all eligibility criteria" = "Yes" then respective patients will be counted as enrolled patients.
- If the question "Did the patient complete the study" = "No" from the Study Completion eCRF form, then respective patients will be counted as discontinued patients.
- If the question "Did the patient complete the study" = "Yes" from the Study Completion eCRF form, then respective patients will be counted as completed patients.

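### SAP sections 15 and 19 replace the protocol's by-term summary of AEs that stopped brolucizumab with a study-exit flag, and define AEs leading to death in two ways

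*SAP*

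**What the plan says.** **Discontinuation.** Protocol 7.6.5, under the primary endpoint analysis, asks for AE incidence by SOC and PT and for similar summaries of several subsets, one of which is "AEs causing discontinuation of study drug".

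The SAP uses a different category. Section 15.2 states that the analysis of "AEs leading to discontinuation from the study by primary system organ class and preferred term is covered in the primary endpoint section 19". Section 19.1.1 then gives the rule: "Primary Reasons for Discontinuation' = 'Adverse event', then corresponding events will be considered as AEs leading to discontinuation from the study". Section 15.1 gives the same rule: "primary reason for discontinuation is 'Adverse Event' then we will consider it as AEs leading to Discontinuation from the study". The reason itself is one entry per patient, as section 10.1 shows: "Patient's primary reason for discontinuation (reasons mentioned in eCRF study completion form) which is as follows". That list holds Adverse event, and also Switch Agent, withdrawal of consent, unsatisfactory effect and Other.

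An event-level item does exist. Among the Action Taken options in SAP 15.1 is "Investigational treatment permanently discontinued due to this adverse event", but it feeds only the overview tables.

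**Deaths.** SAP 15.1 treats an AE as leading to death when the exit reason is Death or the AE outcome is fatal. SAP 19.1.1 uses the fatal outcome alone. Section 15.1 also has a related-death rule that joins the same two conditions and a relationship of Yes with an *or* and an *and*, without brackets.

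SAP 5 says the analysis follows the protocol and lists no departure.

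**The concern.** The protocol asks which events ended brolucizumab treatment. The SAP's table answers which events occurred in patients who left the study for an AE. The first is a property of an event and the second of a patient, and the SAP gives no bridge between them. The table can therefore miss events that belong in it and may include events that do not.

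The death rules raise a similar problem. One section uses a patient-level condition that the other does not, so the two can disagree under the same label, and section 15 can attach a death label to an AE that was not fatal.

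The study is a post-marketing safety commitment to the Indian authority, its primary endpoint is AE incidence and characteristics, and these are among the summaries a safety reader looks at first.

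**Working it through.** No plan figure needs reproducing; the point turns on derivation rules, so I set them side by side and applied them.

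**Step 1. Discontinuation rules compared.**

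| | Protocol 7.6.5 | SAP 15.1, 15.2, 19.1 |
|---|---|---|
| What is stopped | study drug | study participation |
| Level | the event | the patient (single primary reason) |
| Source | not specified | Study Completion form |
| Layout | SOC and PT | SOC and PT |

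**Step 2. Apply them to hypothetical patients.** The SAP-rule column assumes that the exit flag applies to every AE of the patient, since no link to one AE is named.

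| Patient | AEs that stopped the drug (by Action Taken) | AEs flagged by the SAP rule |
|---|---|---|
| One AE stops the drug; exit reason Switch Agent | 1 | 0 |
| Three AEs, one stops the drug; exit reason Adverse event | 1 | 3 |
| One AE stops the drug; patient completes week 56 | 1 | 0 |

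The first row needs only that the investigator records another primary reason. The second depends on how *corresponding events* is read. The third needs a patient who stops treatment but stays in the study.

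**Step 3. Death rules.** Let D = exit reason Death, F = AE outcome fatal, R = related.

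- Section 15.1: D or F. Section 19.1.1: F. They differ only at D = 1, F = 0, that is, a non-fatal AE record in a patient who exits as Death.
- Example: three AEs, one fatal, exit reason Death. Section 15 gives 3 events and section 19 gives 1; both count 1 patient.
- Example: two AEs, neither recorded as fatal, exit reason Death. Section 15 gives 2 events in 1 patient; section 19 gives none.

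**Step 4. Related-death rule in SAP 15.1.** The benchmark is F and R on the same record.

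- Read as (D or F) and R: differs at D = 1, F = 0, R = 1. A non-fatal related AE is labelled a related death.
- Read as D or (F and R): differs at D = 1 whenever F and R are not both 1. This takes in non-fatal AEs, related or not, and a fatal AE that was judged unrelated.

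Under either bracketing a non-fatal AE can be labelled a related death.

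**Step 5. Size of one misclassification.** SAP 8.1 gives 105 enrolled. If all are in the full analysis set, one patient moved into or out of a category changes its incidence by 1/105 = 0.95 percentage points. The number of such patients cannot be derived from the documents.

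**The case against.** Much can be said for the SAP.

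- **The protocol largely merges stopping treatment with leaving the study.** It has one list for both: "Reasons that a patient discontinues treatment and participation from the study are considered to constitute one of the following". Its last assessment is set "at week 56 post-initiation of treatment/or discontinuation of treatment". A reader might infer that the SAP rule systematically misses patients who stop brolucizumab and stay in follow-up. The documents give that thin support: protocol 7.1 rules out re-challenge after intraocular inflammation without saying that the patient leaves, but no section states that such patients continue scheduled visits. This weakens the third patient in the working and leaves the first two untouched.
- **Over-counting is not demonstrated.** *Corresponding events* may be meant as the AE that caused the exit, and the eCRF, which is not among the documents, may carry a link. That stands. What is shown is that the SAP names no such variable, so the rule permits over-counting.
- **The information is not lost.** Drug stops appear in the Action Taken row of the AE and SAE overviews with patients, events and percentages (SAP 15.1, 15.2.1), and SAP 23.4.1 puts eCRF variables into listings. That also stands: the loss is the SOC/PT summary.
- **The section 19 death rule already fits the protocol's request for fatal AEs.** Agreed. The rule out of line is in section 15, and section 19 tables are unaffected by it.

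**Conclusion.** The point holds in two parts. First, the SAP substitutes a study-exit category for the drug-stop category that the protocol requires by SOC and PT, without declaring the change. An AE-driven drug stop recorded under another primary reason is missed, and unrelated AEs may be taken in. Second, sections 15 and 19 define AEs leading to death differently, and section 15 can label non-fatal AEs as leading to death or as related deaths.

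The size is limited. A reader might infer that the primary TEAE incidence is wrong; it is not, because total TEAE counts use neither rule. The frequency of misclassification is unknown, and 0.95 percentage points per patient assumes all 105 are in the full analysis set.

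A reader might also infer that the SAP drops the protocol's AE rates per treatment year. That is not established, because the closing pages of the SAP were not available. The discontinuation point does not rest on such an absence: sections 15.2 and 19.1 state outright which category is tabulated and how.

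This should be corrected before database lock.

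**What to change.** (a) Add to SAP 19 a SOC/PT table of AEs that caused discontinuation of brolucizumab, derived event by event from Action Taken = "Investigational treatment permanently discontinued due to this adverse event". First confirm that the eCRF field records drug discontinuation alongside other actions. SAP 15.1 lists five options, including concomitant medication and hospitalization, so a single-choice field could miss drug stops too. Keep AEs tied to study exit as a separate row.

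(b) Use one event-level death rule in sections 15 and 19: outcome fatal. Define a related death as outcome fatal and relationship Yes on the same record. Before lock, query every patient whose exit reason is Death and who has no AE with a fatal outcome.

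The cost is SAP wording, programming and one check of the eCRF field. Action taken, outcome and relationship are already named in SAP 15.1. The SAP is dated 10 May 2023 and the planned end of data collection was 01 Dec 2023, so on the planned dates there was time to make the change before lock.
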